Note: Recurrent VTE will be defined as inpatient hospitalization with a primary diagnosis of VTE occurring 7 or more days after the first hospitalization discharge date.

- Time (days) from first hospitalization discharge date to first recurrent VTE hospitalization (mean, SD, median, IQR, min, max)
- Time (days) from treatment index date to first recurrent VTE hospitalization (mean, SD, median, IQR, min, max)
- Patients with ≥ 1 hospitalization for major bleeding (ICD-10 codes in CDM; n, %)
- IR of major bleeding (per 100 patient years)

Note: Major bleeding will be defined as inpatient hospitalization with primary diagnosis of gastro-intestinal bleeding, intracranial hemorrhage (ICH) or other major bleeding

- Time (days) from first hospitalization discharge date to first major bleeding episode (mean, SD, median, IQR, min, max)
- Time (days) from treatment index date to first major bleeding episode (mean, SD, median, IQR, min, max)
- Patients with ≥ 1 CRNM bleeding event (n, %)
- IR of CRNM bleeding (per 100 patient years)

Note: CRNM bleeding will be defined as inpatient hospitalization with a secondary diagnosis code for bleeding (without a major bleeding code in the primary position) or an outpatient encounter with a diagnosis code in any position for CRNM GI bleeding or other non-critical types of bleeding. Specifically, it is defined as:

(1) An inpatient admission with a secondary diagnosis for “noncritical site” bleeding such as GI bleeding or other selected noncritical types/sites of bleeding (excluded if major bleeding occurred during the same hospitalization), OR

(2) An outpatient encounter with a diagnosis code for GI bleeding and other selected noncritical types/sites of bleeding.

Any CRNM bleeding events (as described above) that follow a major bleeding event (described above) will not be included in the analysis of CRNM bleeding

- Time (days) from first hospitalization discharge date to first CRNM bleeding episode (mean, SD, median, IQR, min, max)
- Time (days) from treatment index date to first CRNM bleeding episode (mean, SD, median, IQR, min, max)

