9.3. Data sources

IQVIA's CDM database will be linked to Dx and LRx for this analysis.

Hospital Charge Data Master (CDM)

IQVIA's Hospital CDM is comprised of hospital-based data which are sourced from hospital CDM files that roll up to the UB-04 files which are submitted for payment. Data covers non-federal, acute-care short-stay hospitals, covering inpatient and outpatient services, including emergency room (ER) utilization with information on diagnoses, procedures, treatment and daily un-adjudicated charge details. Limited patient and hospital characteristics are also available. Data is available from 2001, with a data lag of approximately 6 weeks. The data cover more than 450 hospitals per month and approximately 8 million inpatient visits and 105 million outpatient visits per year. Charge details during a stay are provided on a daily basis (and lack a time stamp). Diagnoses lack a time or day stamp.

It is important to note some limitations of this dataset. Firstly, because this is an open-source database, there is a loss of visibility to healthcare activity and consumption outside of hospitals that participate in/contribute to the database. Secondly, unlike administrative health plan claims data, it is not possible to apply continuous enrollment (CE) requirements. Proxies for CE must be implemented based on hospital reporting to provide greater assurance that patient healthcare activity within this database is captured during the study period. Socioeconomic details, such as race/ethnicity or income, are unavailable in the data. Clinical detail is also limited. Due to patient privacy reasons, a subject who is 85 years or older will only have the recorded age of "85". And finally, only charges are available in CDM, thus a national cost to charge ratio must be applied to charges.

Medical claims (Dx) database

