IQVIA's Dx database captures over one billion pre-adjudicated claims and three billion records obtained annually from approximately 800,000 office-based physicians and specialists. Dx database is updated on a weekly basis with approximately a 30-60 day lag for data completeness. Key information includes International Classification of Diseases, ninth revision, clinical modification (ICD-9-CM) and International Classification of Diseases, tenth revision, clinical modification (ICD-10-CM) diagnoses, CPT/procedure/Healthcare Common Procedure Coding System (HCPCS) for medical conditions and procedures, date of service, location of care, (pre-adjudicated) charged amount for service, payer types (commercial, Medicaid, Medicare, cash payment), patient age and sex. Note that inpatient data is limited.

Longitudinal Prescription Claims (LRx)

IQVIA LRx database captures information on dispensed prescriptions sourced from retail, mail, long-term care, and specialty pharmacies. These suppliers have direct, long-standing relationships with IQVIA, with many providing data on a daily basis, and all suppliers support weekly data feeds with an ability to provide insight within ten days of the end of each week. This enables IQVIA to ensure that the LRx database has good longitudinal, representative, and current data from consistent and stable suppliers. IQVIA has industry-leading coverage in the following channels: 92% coverage of the retail channel, 72% coverage of standard mail service, and 76% of long-term care facilities. IQVIA receives specialty data directly from the pharmacy resulting in near census data coverage, contributing to greater precision for longitudinal analysis. Additionally, diagnosis is included directly on the majority of specialty pharmacy transactions from the specialty pharmacy providers. An important strength of the LRx database for this analysis is the longitudinal capture of adjudicated and cash prescriptions for all age categories, regardless of insurance type.

Linkage Methodology

A proposed dataset will be constructed utilizing patient data from LRx, Dx and CDM, with the appropriate dataset being selected based upon proportion of linked patients. This process which is compliant with The Health Insurance Portability and Accountability Act of 1996 (HIPAA) is described below:

- IQVIA has developed a patented and proprietary encryption algorithm that utilizes actual patient-level information to create a unique Patient identifier (ID)⁸

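### The CRNM bleeding rule has no exclusion for an outpatient or ER bleeding code shortly before a major-bleed admission, so one episode can count as both CRNM and major

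*Combined protocol and SAP*

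**What the plan says.** All definitions are in section 9.2.2 of the combined protocol and SAP.

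- **Major bleeding:** "Major bleeding will be defined as inpatient hospitalization with primary diagnosis of gastro-intestinal bleeding, intracranial hemorrhage (ICH) or other major bleeding".
- **CRNM bleeding, item (1), inpatient:** an admission with a secondary diagnosis of noncritical-site bleeding, "excluded if major bleeding occurred during the same hospitalization".
- **CRNM bleeding, item (2), outpatient:** "2) An outpatient encounter with a diagnosis code for GI bleeding and other selected noncritical types/sites of bleeding". The lead sentence of the same note allows the code anywhere on the record: "an outpatient encounter with a diagnosis code in any position for CRNM GI bleeding or other non-critical types of bleeding".
- **Sequence rule:** "Any CRNM bleeding events (as described above) that follow a major bleeding event (described above) will not be included" in the CRNM analysis.

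Section 9.3 describes the records that can feed item (2). The hospital charge data (CDM) are described as "covering inpatient and outpatient services, including emergency room (ER) utilization", with the limitation "Diagnoses lack a time or day stamp". The professional claims (Dx) carry "date of service, location of care, (pre-adjudicated) charged amount for service".

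CRNM bleeding belongs to the secondary objective (section 8). It is reported as a proportion, an incidence rate and times to first event (section 9.2.2), and is named among the clinical events in the Cox modelling of apixaban against warfarin (section 9.6).

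**The concern.** GI bleeding appears under both endpoints. For GI bleeds the plan therefore separates major from non-major by care setting and code position, and the rules linking the two endpoints have to keep one episode from entering both. They do this for a bleed coded within the major-bleed stay and for a bleed coded afterwards. They do not do it for an outpatient code recorded just before the stay.

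That order of records is plausible: a patient is seen in an office or ER with a GI bleed and is then admitted with GI bleeding as the primary diagnosis. If the first contact leaves its own record, the major bleed also produces a CRNM event with an earlier date.

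At stake is what the CRNM results mean. Some of the events would be the opening encounter of a major bleed, and the excess would grow with each cohort's major-bleed rate. A difference between cohorts in major bleeding would then carry over in part into the CRNM comparison.

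**Working it through.** The documents state no bleeding rate or event count, so there is no plan figure to reproduce. The check is a reading of the rule, followed by an illustration of scale on assumed inputs.

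**Step 1: code the day before admission.** Take an outpatient GI-bleeding code on day D-1 and an admission on day D with GI bleeding as primary diagnosis.

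- Item (2) is met on D-1.
- The same-stay exclusion does not apply, because it is attached to item (1) only.
- The sequence rule does not apply, because D-1 comes before D.
- Result: one CRNM event on D-1 and one major bleed on D. Nothing else in the documents supplies a look-back window, an episode-linking rule or a precedence of major over CRNM for such a code.

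**Step 2: code on the admission day.** The text does not say whether an event on the same date follows the major bleed. CDM diagnoses carry no time or day stamp, and the Dx description gives a date of service but no time, so the described data cannot order the two. Two programmers could reasonably code this differently.

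**Step 3: what the double count needs.** All of these must hold:

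- a separate outpatient, office or ER record, not one folded into the inpatient stay;
- a GI or other noncritical site (item (2) does not list intracranial bleeding);
- no earlier CRNM event, because section 9.2.2 counts patients at their first event.

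**Step 4: scale.** Let M be the major-bleed rate and C the genuine CRNM rate, both per 100 patient-years. Let q be the share of major bleeds that meet every condition in step 3. All three are assumptions. The observed CRNM rate is approximately C + M × q, so the relative inflation is M × q / C.

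| M | C | q = 0.1 | q = 0.3 | q = 0.6 |
|---|---|---|---|---|
| 2 | 10 | 2% | 6% | 12% |
| 4 | 10 | 4% | 12% | 24% |
| 2 | 20 | 1% | 3% | 6% |
| 4 | 20 | 2% | 6% | 12% |

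Lowest: 2 × 0.1 / 20 = 1%. Highest: 4 × 0.6 / 10 = 24%.

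**Step 5: effect on the CRNM hazard ratio.** Assume a true CRNM hazard ratio of 1.0, a major-bleed hazard ratio of 0.6, warfarin rates M and C = 10, and the same q in both cohorts. Using the ratio of rates, the observed value is about (C + 0.6 × M × q) / (C + M × q).

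- M = 2, q = 0.1: (10 + 0.12) / (10 + 0.20) = 10.12 / 10.20 = 0.99.
- M = 4, q = 0.6: (10 + 1.44) / (10 + 2.40) = 11.44 / 12.40 = 0.92.

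This step takes CRNM bleeding as an outcome modelled on its own. Section 9.6 plans four models but does not list them one by one.

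**The case against.** The strongest reply is that the overlap may be small and that the plan's intent is already clear. Section 9.2.1 lists ER as an admitting source, so an ER arrival may be stored as an attribute of the inpatient stay, where item (1)'s exclusion would catch its codes. Dx is drawn from office-based physicians and records location of care, so the documents do not show that ER professional claims would be classed as outpatient encounters. The two existing safeguards suggest that major bleeding is meant to take precedence, and the sequence rule could be programmed to include the admission date. Finally, a minor bleed treated as an outpatient and a later major bleed can be two real events.

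Most of this stands, and it limits the point. It narrows the ER route, makes the same-day case an ambiguity and not a clear omission, and shows why any window must be short and fixed in advance. It does not close the gap for a separate record dated before admission. Intent inferred from neighbouring rules is not a rule that can be programmed.

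A reader might go further and infer that every major bleed is counted twice, or that the two safety endpoints are no longer distinct. The documents do not support this: the conditions in step 3 must all hold, and the major-bleed results do not change. Nor do they support a large inflation. A figure such as 4 × 0.8 / 8 = 40% needs a high major rate, a low CRNM rate and an 80% duplicate share all at once. It also applies that share to all major bleeds, intracranial included. None of those inputs is in the documents.

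**Conclusion.** The gap is real. As written, the rule classifies a pre-admission outpatient bleeding code as CRNM even when it belongs to the major bleed that follows, and leaves a code on the admission date undecided. The CRNM proportion and incidence rate can be overstated, time to first CRNM bleed can be shortened, and a separately modelled CRNM hazard ratio can be pulled toward the major-bleed one. Major-bleed counts, rates and times are unaffected.

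The size cannot be determined from the documents. The 1-24% inflation and the shift of a true hazard ratio of 1.0 to 0.92-0.99 are illustrations that rest wholly on the assumed inputs in steps 4 and 5. The point concerns one of three events under the secondary objective. It is worth correcting because the rule itself misclassifies and the correction is cheap.

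**What to change.** Add one sentence to the CRNM note in section 9.2.2. It should say that an outpatient or ER encounter with a bleeding code, dated on the admission date of a major-bleeding hospitalization or within a short prespecified window before it (for example 2 days), is part of that major bleed and is not counted as CRNM. Report the number of CRNM events removed, by cohort. The 2 days is a convention with no source in the documents; what matters is that the window is fixed before outcomes are tabulated.

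Leave item 1c of section 9.2 unchanged. It already excludes a patient with either type of bleed between discharge and the treatment index date, so the new rule would do nothing when the admission also falls in that interval. Where the outpatient code comes before the index date and the admission comes after it, the new rule would keep a patient whose bleed began before index and count it as an outcome.

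The cost is one sentence and a date filter in the programming. There are two limits. A rare, truly separate minor bleed inside the window would be lost. And the rule works only when the admission is visible in CDM; sections 9.3 and 9.8 state that care at non-contributing hospitals is not.

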9.2. Variables

[figure not shown]
From the final sample, the following measures will be reported (Figure 2):

1. Patients with a claim for the respective treatment (apixaban for apixaban cohort or warfarin for warfarin cohort; using NDC from LRx) as their first post-discharge outpatient treatment (on or within 30 days following discharge i.e. discharge date or ≤ 30 days after discharge date) (n, %). These patients will comprise the analytic cohort for outcomes assessment.

- a. The date of the first post-discharge outpatient prescription claim in LRx (apixaban or warfarin) will be defined as the ‘treatment index date’ for patients in both cohorts respectively.
 - b. Patients will be required to have pharmacy stability during the 6-month period preceding the treatment index date, defined as consistent reporting of data in each month from the pharmacy associated with the treatment index date in LRx to ensure continuous visibility within LRx. The number of patients excluded due to lack of stability will be reported (n, %)
 - c. Patients with recurrent VTE, major bleeding, or CRNM bleeding between the discharge date and the treatment index date will be excluded. The number of patients excluded due to these reasons will be reported (n, %).
 - d. Patients will be followed from the treatment index date until the earliest of last prescription, last patient medical claim, end of pharmacy stability, or end of study period using the Dx/Rx databases.
2. Patients with OAC (warfarin, apixaban, rivaroxaban, dabigatran, or edoxaban) other than the respective inpatient treatment as their first outpatient prescription claim (on discharge date or within 30 days of discharge) (NDC codes from LRx; n, %). These patients will be captured as having switched from inpatient therapy and will not be further evaluated for outcomes.
 3. Patients with no post-discharge outpatient prescription claim for any OAC (on or within 30 days of discharge) (NDC from LRx; n, %)

All study outcomes will be evaluated for the apixaban and warfarin cohorts.

Figure 2. Study Flow

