9.2.1. Baseline Measures

Baseline demographic, hospitalization and clinical characteristics will be assessed for the apixaban and warfarin cohorts, specifically among patients with their first outpatient index prescription (i.e. treatment index date) and with pharmacy stability. Demographic features will be measured on the patient’s treatment index date. Clinical characteristics will be assessed during the 6-months prior to the treatment-index date. Index hospitalization characteristics will also be assessed and reported for the apixaban and warfarin cohorts.

Baseline demographic characteristics (using LRx data)

- Age (years; mean, standard deviation [SD], median, interquartile range (IQR), min, max)
- Age group (18-34, 35-44, 45-54, 55-64, ≥65 years; n, %)
- Gender (male, female; n, %)
- Payer type (Third party, Medicaid, Medicare, Medicare part D, cash, other; n, %)
- Index date year (2018, 2019, 2020, 2021, 2022; n, %)

090177e19cc79c7fApproved\Approved On: 03-Mar-2023 00:48 (GMT)

- Follow-up duration (mean, SD, median, IQR, min, max)

Hospitalization characteristics (using CDM data)

- Hospital geographic region (Northeast, Midwest, South, West)
- Number of hospital beds (1-99 beds, 100-199 beds, 200-299 beds, 300-499 beds, 500+ beds)
- Hospital location (Rural, Urban)
- Teaching status (Teaching, Non-teaching)
- Admitting source (ER, referral and transfer, routine admission, other, unspecified)
- Discharge disposition (Alive – Home, Left Against Medical Advice or Discontinued Care [LAMA], Transferred – Long Term Care, Transferred – Other Institution, Transferred – Short-Term Hospital, Unknown/Other)
- Index VTE type (DVT only, PE only, DVT and PE; n, %).
- VTE etiology: (Provoked: VTE preceded by hormone therapy, fracture/trauma involving lower extremities, pelvic/orthopedic surgery, or hospitalization for any reason for ≥ 3 days during 3 months prior to index VTE event. Unprovoked: VTE events not classified as provoked)

Baseline clinical characteristics

- Prescribing provider specialty associated with the treatment index prescription in LRx (primary care [general practice/family practice/internal medicine/physician assistant/nurse practitioner], cardiologist, other, unknown; n, %) (Frequency table will be provided with details on provider specialty counts within ‘other’ category)
- Charlson Comorbidity Index (CCI, Dartmouth-Manitoba adaptation; mean, SD, median, IQR, min, max)
- CCI (categorical [0-1, 2, 3, 4+]); n, %)

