- Comorbidities of interest (ICD-10 diagnosis codes in Dx or CDM; n, %)
 - Acquired immune deficiency syndrome (AIDS)
 - Alcohol/drug abuse
 - Anemia
 - Cerebrovascular disease
 - Coronary heart disease/ischemic heart disease
 - Congestive heart failure
 - Chronic obstructive pulmonary disease (COPD)
 - Coronavirus disease 2019 (COVID-19)

090177e19cc79c7f\Approved\Approved On: 03-Mar-2023 00:48 (GMT)

- Dementia/Alzheimer's disease
- Dyspepsia or stomach discomfort
- Diabetes mellitus
- Hemiplegia/Paraplegia
- Hematologic disorders associated with bleeding (thrombocytopenia)
- Hyperlipidemia
- Hypertension
- Inflammatory bowel disease
- Liver/Gall bladder/Pancreatic disease
- Obesity
- Peptic ulcer
- Peripheral vascular disease
- Pneumonia
- Renal disease
- Rheumatologic disease
- Sleep apnea
- Spinal cord injury
- Thrombocytopenia
- Thrombophilia
- Varicose veins
- Procedures of interest (ICD-10 diagnosis or procedure codes, CPT Codes, HCPCS codes in Dx or CDM; n, %)
 - Orthopedic surgery
 - Central Venous Catheter
- Baseline bleeds (ICD-10 diagnosis or procedure codes, CPT Codes, HCPCS codes in Dx or CDM; n, %)
 - Gastrointestinal
 - Intracranial
 - Others
- History of falls (ICD-10 diagnosis codes in Dx or CDM; n, %)
- Fracture/trauma involving lower extremities (ICD-10 diagnosis codes in Dx or CDM; n, %)

- Medications of interest (NDC or HCPCS codes in LRx or Dx; n, %)
 - Angiotensin-converting enzyme (ACE) inhibitors/Angiotensin receptor blockers (ARB)
 - Antiarrhythmic agents
 - Antiplatelet agents
 - Aromatase inhibitors
 - Beta blockers
 - Erythropoiesis stimulating agents (ESA)
 - Gastroprotective agents
 - Nonsteroidal anti-inflammatory drugs (NSAID)
 - Selective estrogen receptor modulators (SERM)
 - Statins

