9.2.2. Outcome measures

The following outcome measures are assessed post-discharge, and will be measured during the variable post-index period starting on the treatment index date for the apixaban and warfarin cohorts.

Treatment patterns

- Persistent days (mean, SD, median, IQR, min, max) will be reported for patients until they discontinue, switch or end of follow-up based on definitions below
- Patients discontinuing outpatient treatment of apixaban or warfarin, respectively (NDC codes from LRx; n, %)

Note: Discontinuation will be defined as the occurrence of a ≥ 30 day gap from the run-out of days' supply of the treatment (post-discharge) index prescription (i.e. apixaban or warfarin) to the date of the next claim for the respective therapy or with no other claims for the respective therapy. The date of the discontinuation will be defined as the last day of the days' supply of the last filled prescription.

- Time (in days) from treatment index date to discontinuation date (mean, SD, median, IQR, min, max)

Note: Kaplan-Meier (KM) curves will be generated to measure median time (and 95 % CI) to discontinuation.

- Patients switching to an OAC other than apixaban or warfarin, respectively (switched) (NDC codes from LRx; n, %)

Note: Patients will be considered to have switched if they filled a prescription for OAC other than apixaban or warfarin, respectively (identified through NDC codes in LRx) or for PAC within 30 days before or after the run out date of index treatment. The date of the switch will be defined as date of the prescription of such a therapy (OAC or PAC).

- Time (in days) from treatment index date to switch date, defined as the date of the first claim for the new OAC or PAC (mean, SD, median, IQR, min, max)

Note: KM curves will be generated to measure median time (and 95 % CI) to switching

Clinical Outcomes

The following clinical outcomes will be assessed during the time patients are persistent with their respective index apixaban or warfarin treatment (treatment index):

- Patients with ≥ 1 hospitalization for recurrent VTE (ICD-10 codes in CDM; n, %)
- Incidence rate (IR) of recurrent VTE (per 100 patient years)
 - The date of the first observed event will be flagged. The numerator for IR will be the number of patients with the event of interest and denominator will be the ‘at risk’ period i.e. the time to first event. The 95% confidence intervals (CI) will also be reported.

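### An outpatient follow-up visit for a bleed already coded at baseline can count as a new on-treatment CRNM bleed, which could raise the CRNM rate by an amount the documents do not let us determine

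*Combined protocol and SAP*

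**What the plan says.** Section 9.2.2 defines CRNM bleeding by an inpatient route (a secondary bleeding diagnosis) and an outpatient route. The outpatient route is "An outpatient encounter with a diagnosis code for GI bleeding and other selected noncritical types/sites of bleeding", and the sentence introducing it makes clear that position does not matter: "an outpatient encounter with a diagnosis code in any position for CRNM GI bleeding or other non-critical types of bleeding". Clinical outcomes are counted from the treatment index date while the patient remains persistent. For the incidence rate, "The numerator for IR will be the number of patients with the event of interest", with person-time running to the first event. This is written under recurrent VTE, and I assume it applies to CRNM bleeding as well.

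Section 9.2.1 tabulates baseline bleeds (gastrointestinal, intracranial, others) as a patient characteristic. The window is given by "Clinical characteristics will be assessed during the 6-months prior to the treatment-index date", and the abstract (Variables) adds that it includes the hospitalization. None of the exclusion criteria in 9.1.2 concerns earlier bleeding.

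Two rules limit what can count:

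- Section 9.2 item 1c: "Patients with recurrent VTE, major bleeding, or CRNM bleeding between the discharge date and the treatment index date will be excluded". The first fill that ends this window must fall "on or within 30 days following discharge i.e. discharge date or ≤ 30 days after discharge date".
- Section 9.2.2: "Any CRNM bleeding events (as described above) that follow a major bleeding event (described above) will not be included in the analysis of CRNM bleeding".

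**The concern.** A bleed produces more than one claim. A patient who bled during the index stay, or in the months before it, may be seen as an outpatient afterwards, and that visit may carry the same diagnosis code. The definition cannot separate such a visit from a new bleed on treatment, and baseline bleeds are described but never used to qualify an outcome event.

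Bleeding on treatment is part of the secondary objective. Because only the first event counts, a carry-over code does three things: it adds a patient to the numerator, it cuts that patient's person-time short, and it displaces any genuine bleed that comes later. The first two raise the rate. If the visits cluster soon after discharge, time to first CRNM bleed is also shortened. A reader of the results could not tell new bleeds from follow-up of old ones.

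**Working it through.** The plan states no expected CRNM rate, baseline-bleed prevalence or follow-up length, so there is no figure to reproduce. The check has two parts: whether any rule blocks carry-over, and how the rate would respond under assumed inputs.

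**1. Do the existing rules block it?**

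Take a bleed coded as a secondary diagnosis in the index stay, and one outpatient visit on day 20 after discharge carrying a qualifying GI bleeding code. Assume the drug supply runs past day 20 for a patient who has already filled.

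| First outpatient fill | Where the day-20 visit falls | Result under the plan |
|---|---|---|
| Day 1 | After index, while persistent | Counted as a CRNM bleed |
| Day 25 | Between discharge and index | Patient excluded (item 1c) |

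The bleed and the visit are the same in both rows. Only the date of the fill decides the classification.

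The rule dropping CRNM codes after a major bleed does not help here. Section 9.2.2 requires a bleeding code as the primary diagnosis for a major bleed, whereas 9.1.1 criterion 1 requires VTE as the primary diagnosis of the index stay. A bleed in that stay can only be secondary, so it never triggers the rule. Recurrent VTE has a separation rule (7 or more days after discharge). Bleeding has none.

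**2. How would the rate respond?**

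All inputs below are assumptions; none comes from the documents.

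- λ: true CRNM rate per patient-year, constant
- T: persistent time in years, the same for everyone
- b: share of the cohort with a baseline bleed
- f: share of those with a carry-over code, placed at t₀ = 30 days (30/365.25 = 0.0821 years)

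Formulas:

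- Without carry-over: events per patient e = 1 − exp(−λT); person-time p = e/λ
- With carry-over: person-time p₀ = (1 − exp(−λt₀))/λ, and every such patient has an event
- Observed rate = [(1 − bf)e + bf] / [(1 − bf)p + bf·p₀]

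With λ = 0.10 and T = 0.5: e = 1 − exp(−0.05) = 0.04877, p = 0.4877, p₀ = 0.0818.

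| b | f | bf | Events per patient | Person-years per patient | Rate per 100 PY | Ratio to true 10.0 |
|---|---|---|---|---|---|---|
| 2% | 10% | 0.002 | 0.0507 | 0.4869 | 10.4 | 1.04 |
| 5% | 30% | 0.015 | 0.0630 | 0.4816 | 13.1 | 1.31 |
| 10% | 50% | 0.050 | 0.0963 | 0.4674 | 20.6 | 2.06 |

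For the same three b/f pairs, with λ from 5 to 20 per 100 patient-years and T from 0.25 to 1 year, the ratio runs from 1.01 (λ = 20, T = 1, lowest pair) to 5.15 (λ = 5, T = 0.25, highest pair). In this model the direction is upward whenever bf is above zero. The size depends entirely on inputs that the plan does not contain.

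**The case against.** Much of the case for leaving the plan alone is sound.

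- **The scope is limited.** Not every outpatient bleeding code counts. The code must be for GI or selected noncritical bleeding, fall in persistent time, be the patient's first, and not follow an outcome major bleed. Item 1c removes part of the carry-over. The list behind the selected codes is not in the document and could narrow the problem further. This stands, but none of it closes the gap for an early filler.
- **No size is shown.** A reader might take 5–15% with a baseline bleed, 20–40% of them with a coded follow-up visit, and a true cumulative incidence of 8%, and infer an inflation of 1/8 to 6/8, or 13% to 75%. All three inputs are assumed. The product also counts intracranial baseline bleeds that cannot carry over to a noncritical code, makes no deduction for item 1c, and ignores overlap with true events. The documents do not support that figure.
- **The Cox models.** A reader might infer that baseline bleed will appear as a strong predictor, or that the apixaban–warfarin hazard ratio is biased. Section 9.6 only lists covariates to be considered, possibly with backward elimination, and nothing in the documents says that baseline bleeding or fill timing differs between cohorts. Equally, including baseline bleed as a covariate would not correct a misclassified outcome or the descriptive rate.
- **The VTE separation rule.** The protocol does not give its reason, so it shows a contrast, not an admitted carry-over problem for bleeding.
- **Rewriting the definition has its own cost.** A 30-day same-site look-back would miss older bleeds and later visits, and could suppress genuine early re-bleeds on an anticoagulant. It also lacks a date for index-stay bleeds, because 9.3 says CDM diagnoses carry no day stamp. This is a good reason to leave the primary definition alone.
- **Section 9.8 already admits possible misclassification.** It does so in general terms and does not mention this mechanism.

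**Conclusion.** The gap is real. As written, an outpatient visit that follows up a baseline or index-stay bleed can be counted as a first CRNM bleed on treatment, and item 1c prevents this only for codes that fall before the first fill. The CRNM incidence rate could be biased upward and time to first CRNM bleed shortened. The conclusion rests on reading the first-event rule as applying to CRNM bleeding, and on some patients with a baseline bleed having a coded follow-up visit while persistent.

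The documents do not show how large the effect is. It could be negligible (ratio 1.01) or substantial (5.15) across the assumed grid. Nor do they show that the treatment contrast is affected. The point concerns the interpretability of one component of the secondary objective, and an added analysis is enough to deal with it.

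**What to change.** Keep the CRNM definition in 9.2.2 and item 1c as they are. Add to 9.2.2 and 9.6 a prespecified analysis along these lines:

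*The number of patients with CRNM bleeding, the incidence rate, time to first event and the CRNM Cox model will also be reported separately for, or excluding, patients with a GI or other noncritical bleeding code in the six-month baseline, including the index hospitalization.*

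The baseline bleed flags in 9.2.1 supply the grouping. State in advance how the result will be read: patients with a baseline bleed may also have a higher true risk, so the difference between groups shows how much of the rate could be carry-over and does not measure it.

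A same-site clean-period rule may be added as a sensitivity analysis only, with its length fixed beforehand. Index-stay bleeds should be anchored at the discharge date, since CDM diagnoses cannot be dated within the stay.

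The cost is one extra table and a sentence or two in each section, with no new data. The restricted set loses some precision. It will not be wholly free of carry-over, because care at sites that do not contribute data is unseen and prior bleeds may go unrecorded.
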